### **Interim Analysis**

Our study does not entail any sequential or adaptive trial designs and as such requires no interim analyses.

## **7.3 Subject Population(s) for Analysis**

Only patients who are randomized into the study and have necessary baseline values for primary and secondary outcomes will be included in the analyses.

## **8 Safety and Adverse Events**

### **8.1 Adverse Events:**

The investigator/study team will report to the Mayo IRB any UPIRTSOs and NonUPIRTSOs according to the Mayo IRB Policy and Procedures.

An adverse event is defined as an untoward or undesirable experience associated with the use of a medical product (i.e. drug, device, biologic) in a patient or research subject. All adverse events that are considered related to the direct use of liposomal bupivacaine will be defined, collected, and reported.

The principal investigator will be responsible for determining whether an event is related to the direct use of liposomal bupivacaine. An AE will be considered unexpected if the nature, severity, or frequency of the event is not consistent with the risk information previously described for the standard of care procedure or in the package insert for liposomal bupivacaine.

All study-related AEs will be followed until stabilization or resolution.

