### 3.4 Primary Safety Endpoints

All patients will be continuously monitored for local anesthetic toxicity or other reaction to liposomal bupivacaine for the entire surgical scope of care. During surgery, standard ASA monitors will be in place. In the PACU, vital signs will be obtained every 15 minutes with continuous telemetry and pulse ox, with a minimum 2:1 RN monitoring. Continuous surveillance will be exercised for medication reaction or local anesthetic toxicity including but not limited to: tinnitus, perioral numbness, mental status changes, cardiac arrhythmia, respiratory compromise, rash, or hives. 20% intralipid for treatment of toxicity will be available at all times. In addition, patients will be monitored for signs of pneumothorax related to the peripheral nerve block including but not limited to: dyspnea, oxygen desaturation, or hemodynamic instability. At discharge, patients will be educated regarding signs and symptoms for local anesthetic toxicity and instructions to call the on-call physician with mild symptoms and present to the ED if moderate or severe symptoms.

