##### Control Group:

In this group, all peripheral nerve blocks will be performed with ultrasound guidance by an attending anesthesiologist experienced in the technique, or experienced anesthesiology

resident with direct attending supervision and assistance. Standard bupivacaine will be utilized. 25 ml of 0.5% bupivacaine for peripheral nerve block will be utilized. Further, 8 mg (2 ml) IV dexamethasone will be administered concomitantly at the time of the block.

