### 6.5 All Time Points

If patient non-compliance with electronic surveys is identified, the study coordinator will attempt to contact non-compliant patient to either encourage him/her to either complete the surveys, or to directly obtain respective data points from them. Further, patients who are given diaries will receive daily reminder phone calls from the study coordinator in the 72 hours following discharge.

Complications will be recorded. These include cardiac arrest, acute respiratory failure, venous thromboembolism event, ileus, SSI, deep infections, urinary tract infection, nerve injury, pneumothorax.

Schedule of Events				
Study Activity	Pre-op Visit	Surgical Stay	Time from discharge to first post-op visit	Post-op Visit
Study Agent Administration		X		
Informed consent	X			
Randomization		X a		
Demographics	X			
History / Physical Exam	X			
Concurrent Meds	X			
Pain Scores	X	X	X	X
PROMs b	X			X
Satisfaction Scores c			X	X
Opioid Use		X	X	X
Adverse Event Evaluation		X	X	

a: In pre-op, will be performed by pharmacy  
 b: ASES, SANE, SST, VR-12 scores  
 c: Obtained at 72 hrs post-op and at 1st post-op visit

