### **8.3 Medical Monitoring:**

It is the responsibility of the Principal Investigator to oversee the safety of the study at his/her site. This safety monitoring will include careful assessment and appropriate reporting of adverse events as noted above, as well as the construction and implementation of a site data and safety-monitoring plan. Medical monitoring will include a regular assessment of the number and type of serious adverse events.

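### Section 8.1 records an adverse event only if it is attributed to liposomal bupivacaine, so milder toxicity and drug reactions cannot be validly compared between arms

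*Combined protocol and SAP*

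**What the plan says.** Section 8.1 sets the collection rule: "All adverse events that are considered related to the direct use of liposomal bupivacaine will be defined, collected, and reported". It also says who applies it: "The principal investigator will be responsible for determining whether an event is related to the direct use of liposomal bupivacaine". There is no matching rule for plain bupivacaine, for the block as a procedure, or for events judged unrelated.

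Other sections bear on safety data:

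- Section 3.4, headed as the primary safety endpoints, covers both arms: "All patients will be continuously monitored for local anesthetic toxicity or other reaction to liposomal bupivacaine for the entire surgical scope of care". It lists what to look for: "Continuous surveillance will be exercised for medication reaction or local anesthetic toxicity including but not limited to: tinnitus, perioral numbness, mental status changes", and goes on to arrhythmia, respiratory compromise, rash and hives. It adds that "patients will be monitored for signs of pneumothorax related to the peripheral nerve block".
- Section 6.5 applies to all time points and has no arm or causality condition: "Complications will be recorded. These include cardiac arrest, acute respiratory failure, venous thromboembolism event, ileus, SSI, deep infections, urinary tract infection, nerve injury, pneumothorax". The Schedule of Events in that section has an adverse event evaluation row for the surgical stay and the period after discharge.
- Section 8.3 states: "Medical monitoring will include a regular assessment of the number and type of serious adverse events".
- Section 5.2, on the control arm: "25 ml of 0.5% bupivacaine for peripheral nerve block will be utilized".
- Section 5.6 blinds patients, recovery staff, data collectors and statisticians. It names the administering anesthesiologist and pharmacy as unblinded, and has every patient charted as having received liposomal bupivacaine. The principal investigator appears in neither list.
- Section 7.2 has no analysis of adverse events or complications.

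**The concern.** A rule that decides whether an event is recorded should not depend on a causal judgement about one arm's drug. Here it does, and the comparator is an active local anesthetic with risks of the same kind. A reaction to plain bupivacaine in a control patient is not, in fact, related to liposomal bupivacaine. Whether it enters the data depends on what the investigator believes the patient received and how the investigator reads the event.

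At stake is the comparability of the drug-reaction data that section 3.4 places under its safety endpoint heading. If events judged unrelated are never written down, nobody can later re-examine the attribution or tabulate all events by randomised arm. The pain, opioid and block-duration outcomes are not affected.

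**Working it through.** The plan gives no figure for adverse events, so there is none to reproduce. The check is mainly a reading of sections against each other, with two short calculations.

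**1. Are controls exposed to the same class of risk?** Inputs are from section 5.2, using 0.5% = 5 mg/ml and 0.25% = 2.5 mg/ml.

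- Control arm: 25 ml × 5 mg/ml = 125 mg plain bupivacaine.
- Liposomal arm, plain component: 7.5 × 5 + 7.5 × 2.5 = 37.5 + 18.75 = 56.25 mg, alongside 133 mg liposomal.
- Ratio of plain bupivacaine, control to liposomal arm: 125 / 56.25 ≈ 2.2.

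Section 1.3 lists central nervous system, cardiovascular and allergic reactions as risks of bupivacaine-containing products in general. By the protocol's own account, such events can occur in controls. These figures show exposure only; they do not show how many events would be missed.

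**2. Which section 3.4 signs have a recording rule without a causality filter?**

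| Sign or event in 3.4 | Named in 6.5? | Rule otherwise |
|---|---|---|
| Pneumothorax | Yes | – |
| Respiratory compromise | Only as acute respiratory failure | 8.1 filter |
| Cardiac arrhythmia | Only as cardiac arrest | 8.1 filter |
| Tinnitus, perioral numbness, mental status changes | No | 8.1 filter |
| Rash, hives | No | 8.1 filter |

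Section 3.4 describes surveillance and response, and does not say what is to be recorded. The schedule's evaluation row says when events are assessed, not which ones count; 8.1 supplies that. Section 8.3 concerns serious events, and its reporting refers back to the preceding text.

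**3. What does the filter do to a control patient's event?**

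- If the principal investigator is blinded, the chart says liposomal bupivacaine was given. The event is either attributed to a drug the patient did not receive and recorded, or judged unrelated and not recorded.
- If the principal investigator knows the assignment, the event cannot be related to liposomal bupivacaine and falls outside the rule.
- In both cases, events judged unrelated are lost in both arms.

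**4. What could a complete record show?** With zero events in n patients, the exact one-sided 95% upper bound is 1 − 0.05^(1/n).

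- n = 50 (section 3.2): 1 − 0.05^(1/50) = 5.8%.
- n = 55 (110 randomised equally, section 5.3): 1 − 0.05^(1/55) = 5.3%.

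For a comparison of two proportions, I assumed event rates (none are in the documents), two-sided alpha 0.05 and the normal approximation: power = Φ[(|p1 − p2| − 1.96·√(2p̄(1 − p̄)/n)) / √((p1(1 − p1) + p2(1 − p2))/n)], where p̄ is the mean of p1 and p2.

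| Assumed rates | Power, n = 50 | Power, n = 55 |
|---|---|---|
| 5% vs 15% | 38% | 41% |
| 5% vs 25% | 81% | 85% |

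Full collection would therefore support description and detection of large differences, and little more.

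**The case against.** A reader might infer more than the documents support: that nothing else is collected, that a control patient cannot have a recordable event by definition, that the control count is therefore zero by construction, and that safety cannot be compared at all. The case against that reading is good.

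- Section 6.5 records complications in every patient without a causality test. Cardiac arrest, acute respiratory failure, nerve injury and pneumothorax are among the nine named, so the gravest events can be compared by arm. The list may also not be exhaustive.
- Section 8.1 opens with reporting to the review board that is not limited to liposomal bupivacaine, and 8.3 adds review of serious events.
- Section 5.6 does not list the principal investigator as unblinded and has all patients charted as receiving liposomal bupivacaine. Section 4.3 suggests that the principal investigator is not the person giving the block. A blinded investigator could attribute a control patient's event to the liposomal drug, so a structural zero does not follow.
- Section 2 has no safety objective and 7.2 no safety hypothesis, so the trial does not claim a formal safety comparison.

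All of this stands against the stronger reading. It does not remove the narrower defect. An open-ended complications list does not direct staff to enter tinnitus or a rash, when 8.1 gives an explicit and narrower rule for adverse events. Blinding removes knowledge of the arm, but it leaves the investigator judging relatedness to a product that about half the patients never received, with the answer deciding whether the event is recorded. The absence of a planned test does not excuse a filtered record, because a descriptive table by arm needs complete collection too.

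**Conclusion.** The point holds for a defined set of events: local anesthetic toxicity signs, arrhythmia short of arrest, respiratory compromise short of acute failure, rash, hives, and any other adverse event outside the 6.5 list. For these, the only recording rule is conditional on attribution to one arm's drug, and counts by arm are not a valid basis for comparison. It does not hold for the nine complications in 6.5.

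The number of events lost, and the direction of any bias, cannot be derived from the documents. The conclusion rests on reading 8.1 as the operative definition for the schedule's adverse event evaluation. It does not depend on whether the principal investigator is blinded: section 5.6 suggests so without stating it, and the rule fails either way. The 5.3% to 5.8% bounds describe the limits of arms of this size; they do not measure the defect.

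This should be corrected because it is a stated rule that yields an incomplete and possibly biased record if followed, and it is cheap to change. It does not threaten the primary outcome.

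**What to change.** 1. In 8.1, collect adverse events in both arms regardless of attribution, and name the 3.4 toxicity and reaction signs as events to be recorded.
2. Record relatedness to the study block (either drug) as an attribute of each event, not as a condition for recording it. State that the assessor is blinded, and say in 5.6 whether this covers the principal investigator.
3. Align 6.5 and its schedule with the new 8.1 wording, so that complications and adverse events follow one rule.
4. Add to section 7 a descriptive table of adverse events and complications by randomised arm, with counts, percentages and exact confidence intervals, and no formal test.

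The cost is protocol wording, a few more case report form entries and a small data-entry load. No new visits are needed, since 3.4 already requires the observation and the schedule already has the evaluation. The limitation to state alongside the table is that, with 50 to 55 patients per arm, it can describe but will rarely discriminate.

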### **8.2 Adverse Event Reporting Period:**

For this study, the study treatment follow-up period is defined as 7-10 days after the procedure when they are contacted by the study team.

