## 3 Study Design

### 3.1 General Description

This will be a prospective, single-blinded randomized clinical trial comparing outcomes in patients undergoing total shoulder arthroplasty (anatomic and reverse) who receive a peripheral

[figure not shown]
nerve block with liposomal bupivacaine in combination with standard bupivacaine versus standard bupivacaine alone. Subjects will be screened in the outpatient clinic upon initial patient election to proceed with shoulder replacement surgery. Interested and qualified patients meeting all inclusion criteria will be offered the opportunity to participate in this study. Once consent is obtained, baseline characteristics will be recorded and patients will be randomized to intervention or control. Following surgery, patients will be followed until their 3-week post-operative visit.

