### 3.3 Duration of Participation

The duration of time that patients can expect to be directly involved in the study is 3-weeks; i.e. initial surgery up until the first post-operative visit at 3-weeks.

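### The adverse-event window is inconsistent: Section 8.2 ends it at an unscheduled day 7-10 contact, the schedule runs it up to but not including the 3-week visit, and Section 6.5 sets no cut-off

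*Combined protocol and SAP*

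**What the plan says.** The combined protocol and SAP addresses the timing of safety collection in several places.

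- **Section 8.2 (Adverse Event Reporting Period):** "the study treatment follow-up period is defined as 7-10 days after the procedure when they are contacted by the study team".
- **Sections 3.1 and 3.3:** "patients will be followed until their 3-week post-operative visit", and participation is described as "initial surgery up until the first post-operative visit at 3-weeks".
- **Section 6.5, Schedule of Events:** the row "Adverse Event Evaluation" is ticked under Surgical Stay and under "Time from discharge to first post-op visit". It is blank under Pre-op Visit and Post-op Visit.
- **Section 6.5, text under the heading for all time points:** "Complications will be recorded. These include cardiac arrest, acute respiratory failure, venous thromboembolism event". The list goes on to surgical-site and deep infection, nerve injury and pneumothorax, among others. No end date is given.
- **Section 6.4 (3-week visit):** opioid use, pain, satisfaction and patient-reported outcomes are collected. No AE or complication item is listed.
- **Section 8.1:** "All study-related AEs will be followed until stabilization or resolution".

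**The concern.** Three places define when safety information is collected, and they give three different windows. Section 8.2 stops at a contact between day 7 and day 10. The schedule carries on to the 3-week visit but does not include it. Section 6.5 has no stopping point. The contact on which Section 8.2 relies appears nowhere in the study procedures, while the 3-week visit, which is in the procedures, has no AE item.

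What is at stake is how complete and how uniform the safety data are. One coordinator could reasonably close AE collection at day 7, another at day 10, and a third could ask at week 3, each following some part of the protocol. Section 1.3 names persistent anesthesia, paresthesias and nerve injury among the risks, and Section 6.5 names infection and thromboembolism as complications to record. Whether a deficit has persisted or an infection has appeared by week 3 is something the week-3 visit could establish. Complication counts gathered over differing windows would be hard to interpret. No primary or secondary efficacy outcome depends on this.

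**Working it through.** The documents give no figure for the share of follow-up covered by AE collection, so there is none to reproduce. The check is a short calculation followed by a comparison of the sections.

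**Step 1. Share of follow-up outside the Section 8.2 window**

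Inputs:
- total follow-up T = 3 weeks = 21 days from surgery (Sections 3.1 and 3.3);
- end of the Section 8.2 window d = 7 to 10 days after the procedure.

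Formulas: days outside = T − d; share outside = (T − d)/T.

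| d | Days outside | Share outside | Share inside |
|---|---|---|---|
| 7 | 21 − 7 = 14 | 14/21 = 66.7% | 7/21 = 33.3% |
| 10 | 21 − 10 = 11 | 11/21 = 52.4% | 10/21 = 47.6% |

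**Step 2. The windows side by side**

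| Source | What is collected | End of window | Covers days 10-21? | Covers the 3-week visit? |
|---|---|---|---|---|
| Section 8.2 | AEs | day 7-10 contact | No | No |
| Schedule, AE row | AEs | up to the first post-operative visit | Yes | No (blank) |
| Section 6.5 text | named complications | none stated | Yes | Yes, by its heading |
| Section 6.4 | 3-week visit content | not applicable | not applicable | No AE item listed |

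No two of the first three sources give the same end point.

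**Step 3. Which dated contacts could carry an AE question**

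Post-discharge contacts described in Section 6:
- twice-daily e-mailed pain surveys, within the first 72 hours after surgery (6.3);
- a satisfaction survey at 72 hours (6.3);
- daily opioid surveys or diary, within the first 72 hours (6.3);
- calls to patients who do not complete surveys, and daily diary reminder calls in the 72 hours after discharge (6.5);
- the 3-week visit (6.4).

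No AE question is described for any of them. The only dated post-discharge contact tied to AEs is the one in Section 8.2, and it is missing from this list. Its dates do fall inside the ticked interval column, so that tick may be meant to include it, but nothing says so. After day 10 the interval tick has no dated contact behind it, and the next contact, the 3-week visit, has no AE tick. Section 3.4 adds discharge education on toxicity symptoms and whom to call. That relies on the patient to report, and it does not mention infection or thromboembolism.

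**The case against.** The strongest case on the other side has four parts.

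1. **The later period is nominally covered.** A reader might infer from Section 8.2 and the blank at the 3-week visit that the last half or more of follow-up has no planned AE assessment, or that nothing is scheduled after 72 hours. The documents do not support this. The schedule ticks AE evaluation for the whole interval up to the first post-operative visit, which includes days 10-21, and Section 6.5 records named complications without a cut-off. It would likewise go too far to say that nobody is meant to make the day 7-10 contact, because Section 8.2 assigns it to the study team. This part stands and limits the point to an inconsistency.

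2. **There may be two separate streams.** Section 8.1 confines reported AEs to those judged related to liposomal bupivacaine, while Section 6.5 covers complications generally. On that reading the Section 8.2 limit does not restrict Section 6.5. This is possible, but the protocol does not state it. It would also leave Section 8.2 at odds with the AE row of the schedule, and would not explain how complications are captured at a visit whose content list omits them.

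3. **Events are followed to resolution.** Section 8.1 does carry an identified event, such as a persisting nerve deficit, beyond day 10. It does not provide for finding an event that first appears, or is first noticed, after that.

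4. **The length of the window is a design choice.** The protocol describes drug delivery of up to 72 hours, and 7-10 days is well beyond that. A window shorter than follow-up is not an error in itself. What stands is that the plan does not choose one window and apply it throughout.

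**Conclusion.** The point holds as an inconsistency in the AE collection window. Section 8.2 leaves 11 to 14 of 21 days (52-67%) outside its window, while the schedule and Section 6.5 extend beyond it on different terms. The contact that closes the Section 8.2 window is not described in Section 6 and has no column of its own. No dated contact that asks about AEs is described after day 10, including at the 3-week visit.

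The percentages measure the Section 8.2 window only, not total safety capture. A reader might also take the point to mean that late infections, thromboembolism or nerve injuries will go unrecorded. The documents do not show that, because Section 6.5 calls for them to be recorded. What is missing is a stated occasion and a uniform way of asking.

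The conclusion assumes that the sentence in Section 8.2 defines the AE reporting period, as its heading indicates. It also takes 3 weeks as 21 days from surgery, and the blank cell at the Post-op Visit as the plan's intent. The absence of an AE item in Section 6.4 supports that last reading. The change is worth making because it improves safety capture at almost no cost, although no efficacy result depends on it.

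**What to change.** - Reconcile Sections 8.2, 6.4, 6.5 and the Schedule of Events to one AE and complication collection window that runs to the existing 3-week visit.
- Tick AE evaluation at the Post-op Visit and add the item to Section 6.4, using the same structured question in both arms. This matters because Section 8.1 frames AEs by their relation to liposomal bupivacaine, which control patients do not receive.
- Either itemise the day 7-10 contact in Section 6 and the schedule, saying what is asked, or remove it from Section 8.2.
- If AEs and complications are meant to be separate streams, say so and give each its own window.

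The cost is protocol wording and one extra question at a visit that is already planned. No new visit is needed, and treatment, sample size and efficacy analysis are unchanged.
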